17.9 Clinical Outcome Measurements

All other clinical outcome measurements will be analyzed for the ITT AZD7442 600 mg IM or IV treated groups for both solid tumor and hematologic malignancy population with a Per-Protocol (PP) sensitivity analysis. These include:

- Rate of symptomatic SARS-CoV-2 infection including hospitalization and/or death
- Rate of adverse events reported by the patient or investigator across the entire study observation period
- Rate of symptoms and change from baseline in symptom severity over the observed time points. Correlation of symptom severity with log-adjusted serum concentration of AZD7442 levels, defined as the change over time from first measurement at Day 30 to Days 90, 180, 270 and 360.
- Change in log-adjusted serum concentration of AZD7442 levels, defined as the change over time from first measurement at Day 30 to Days 90, 180, 270 and 360, relative to change in clinical status for individual disease category cohorts
- Clinical treatment outcomes such as treatment discontinuation and time to treatment progression where possible
- Health care resource utilization rates for ER, urgent care, hospitalization and unplanned telehealth visits
- Rate of death will also be considered if there is sufficient information for analysis
- Factor analysis to determine which factors (e.g., age, gender, type of cancer, cancer duration, type treatment, etc.) are related to higher levels of serum concentration of AZD7442

	
17.10 Breakthrough Infection Descriptive Analysis
 
All patients who experience a symptomatic breakthrough SARS-CoV-2 infection, defined as a positive SARS-COV-2 RNA by RT-PCR test with or without viral genomics and/or symptomatic clinical evidence of SARS-CoV-2 disease, will have a descriptive analysis that includes a clinical outcome (e.g., symptomatic infection, SARS-CoV-2 related hospitalization and/or SARS-CoV-2 related death), a profile of neutralizing antibody as measured by serum concentration of AZD7442, a functional analysis of T- characterized by cytokine stimulation and secretion and a genomic sequencing of the virus. In addition, relationship between these data and World Health Organization Ordinal Scale for Severity of SARS-CoV-2 Disease will be performed.
 
17.11 Patient Demographics, Disease and Treatment Attributes
 
Baseline patient characteristics for all enrolled participants include age, gender, race, weight and Body Mass Index (BMI) and will be analyzed using descriptive statistics for all strata and sub-strata. Patient demographics, disease and treatment attributes will be summarized and compared between the disease category cohorts and concomitant treatment regimens. Any attributes with significant differences will be considered for inclusion as factors in logistic regression and linear model analyses. Disease attributes will include stage of disease, time from initial diagnosis and performance status will be assessed. Treatment regimen attributes including type of therapy, cycle at time of study enrollment and cycle duration will be summarized.
 
17.12 Statistical Models
 
Statistical considerations for other endpoints will be treated on a case-by-case basis depending on the nature of the outcome variables and their distributions. Such approaches may include χ^2 cross-tabulations, t-tests, ANOVAs, negative-binomial regressions, logistic regressions, mixed model for repeated measures and linear regression.

18.0
	
18.1 Identification of Non-Serious and Serious Adverse Events


Safety and Adverse Events Analyses
	
Patient safety, non-serious and serious adverse events will be determined using Patient Experience/COA survey data, physician-reported events and lab data for all qualified patients treated with either chemotherapy only, immunotherapy only, targeted therapy only, or other therapy/combination therapy only. Individual symptom severity is assessed on a 3-point scale. In this study, safety will be assessed by evaluating non-serious and serious adverse events, chest x-rays, bacterial cultures, SARS-COV-2 RNA by RT-PCR and viral genomic test results. In addition, important infectious and oncologic safety events will be reviewed from CEC-adjudicated data for symptomatic SARS-CoV-2 infection including SARS-CoV-2 related hospitalization and SARS-CoV-2 related death.
 
18.2 Available Data
 
Safety data such as physical exams, labs and ECG data that are completed during the course of routine clinical care will be available to the MediMergent medical monitor through individual patient EMR data. Collection of non-serious adverse events will be limited only to answers on the follow-up survey questions as follows: (1) related to any event that occurred in the first 24 hours post AZD7442 administration, (2) symptoms of SARS-CoV-2 infection, (3) positive PCR-RT SARS-COV-2 test, (4) any unplanned telehealth visit, (5) any non-routine office visit, and/or (6) any ER/Urgent Care visit. Such events will be documented on the nonserious adverse event form. PCR test results will be reported digitally from the testing lab to the study site and the study site will report this result to MediMergent. If the Investigator considers that there was a causal relationship between treatment with AZD7442 or protocol design/procedures and a patient’s underlying disease progression, then this must be reported as an AE or SAE.
 
For all Serious Adverse Events, a separate data collection form, based on AstraZeneca guidelines, will be completed by the study site and submitted to MediMergent for data input and analysis. All Serious Adverse Events require collection of source documentation for review by the MediMergent safety team. Reporting of Adverse Events and Serious Adverse Events will follow FDA Guidelines and AstraZeneca reporting procedures.

--	---

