	
 • Assess the relationship between type of cancer (solid vs. hematologic) and T-cell function in immuno-suppressed cancer patients at 30 days post administration of AZD7442. • In immuno-suppressed cancer patients who are subsequently diagnosed as having symptomatic SARS-COV-2 RNA by RT-PCR positive SARS-CoV-2 infection, assess the immunologic profile relating to AZD7442 serum level and T-cell function at the time of RT-PCR positive SARS-CoV-2 infection. • Assess the relationship between change from Day 30 in AZD7442 serum level, T- cell function and World Health Organization Ordinal Scale (WOS) for COVID-19 disease severity in the aggregated immune-suppressed cancer patients with documented SARS-COV-2 RNA by RT-PCR positive SARS-CoV-2 infection. • Assess the relationship between change from Day 30 in AZD7442 serum level, T- cell function and World Health Organization Ordinal Scale (WOS) for COVID-19 disease severity in immune-suppressed cancer patients with documented SARS-COV-2 RNA by RT-PCR positive SARS-CoV-2 infection based on cancer treatment. • Assess the relationship between change from Day 30 in AZD7442 serum level, T- cell function and World Health Organization Ordinal Scale (WOS) for COVID-19 disease severity in immune-suppressed cancer patients with documented SARS-COV-2 RNA by RT-PCR positive SARS-CoV-2 infection based on type of cancer.
	
5.1 Overall Study Design
 
This study is a multi-center, prospective, pragmatic evaluation of AZD7442 600 mg IM or IV for prevention of SARS-CoV-2 infection including SARS-CoV-2 related hospitalization and/or SARS-CoV-2 related death in cancer patients. All qualified patients will receive active AZD7442 drug.
 
5.2 Screening Evaluation
 
Assessing the general level of immune competence in a patient includes: disease severity, duration, clinical stability, complications, comorbidities, and any potentially

**5.0
Study
Design**

immune-suppressing treatment. The study begins with a screening evaluation of solid tumor or hematologic malignancy patients actively or previously treated for their oncologic disease. Enrollment will include patients who fulfill at least one of the following criteria (see Section 8.1; Inclusion Criteria):

- Having received chimeric antigen receptor (CAR)-T-cell or hematopoietic stem cell transplant (within 2 years of transplantation or taking immunosuppression therapy)

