9.3 Follow-Up Activities

Follow-Up activities are as follows:

- At Day 180 post-baseline, all patients will be administered a repeat dose of AZD7442 600 mg IM or IV. The window for this treatment will be +/- 5 days from the actual due date. The dose will be administered in the same manner as the baseline dose unless patient circumstances require a different route of administration. All requirements listed above for baseline AZD7442 administration both IV and IM will be followed for the repeat dose including the one-hour post-dose observation period.
- Patients will complete follow-up Patient Experience/COA surveys on days 2, 30, 60, 90, 120, 150, 180, 181, 210, 240, 270, 300, 330 and 360 post-baseline at home. The window for these surveys will be +/- 5 days from the actual survey due date except for day 2 survey which is +5 days only.
*NB - Study participants will complete all surveys via mobile phone, desktop, laptop, tablet computer or via Call Center. The study site is not responsible for patient completion of the surveys.
- Patients will complete QoL assessments on days 2, 30, 90, 180, 270, and 360 post-baseline at home. The window for these assessments will be +/- 5 days from the actual due date except for day 2 assessment which is + 5 days only.
- Site personnel will obtain blood for serum concentration of AZD7442 at days 30, 90, 180, 270 and 360 post-baseline in the office for all patients. The window for these blood draws will be +/- 5 days from the actual due date. All

serum concentration measurements will be sent to PPD Bioanalytical Laboratory in Richmond, VA for analysis.

- Site personnel will obtain blood for RBD-IgG antibody level at days 90, 180, 270 and 360 post-baseline in the office for all patients. The window for these blood draws will be +/- 5 days from the actual due date. All RBD-IgG antibody levels will be sent to LabCorp for analysis.
- Site personnel will obtain blood for T-cell assay at Day 30 post-baseline in the office for all patients and send to Isoplexis in Branford, CT for analysis. A subset of patients will be selected including 120 patients with hematologic malignancy and 60 patients with solid tumors in order to have site personnel obtain blood for repeat T-cell assay at Day 210 post-baseline in the office and send to Isoplexis in Branford, CT for analysis. The window for these blood draws will be +/- 5 days from the actual due date.

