
15.0 Interim Analysis
	
the analysis will determine which group is more likely to experience such infections.
 
An interim analysis will be performed after the first 6-month assessments are completed for the first 50% of the targeted patient sample for each malignancy, i.e., 750 patients including 600 solid tumor and 150 hematologic malignancies. The primary endpoint of the interim analysis will be the serum concentration of AZD7442 for all patients with comparisons between disease categories.
 
Secondary analyses will be conducted on the following measures in all patients included in the interim analysis set:
 
 • Incidence of break-through infections in all patients and then sub-divided into solid tumor and hematologic malignancy. • Time to infection compared between solid tumor and hematologic malignancy • RBD-IgG levels for all patients with comparisons between disease category • CD4/CD8 levels for all patients with comparisons between disease category

16.0 Immunological Sub-Study Endpoints
	
16.1 Immunologic Sub-Study Endpoints
 
 • Comparison of CD4 T-cell and CD8 T-cell function in all cancer patients at 30 days post initial administration of AZD7442 to similar tests performed in normal healthy donor subjects • Comparison of the relationship between different cancer treatment regimens and T-cell function in all cancer patients at 30 days post administration of AZD7442 • Comparison of the relationship between type of cancer (solid vs. hematologic) and T-cell function in all patients at 30 days post administration of AZD7442 • Comparison of the immunologic profile relating to AZD7442 serum level and T-cell function at the time of PCR positive SARS-CoV-2 infection in all cancer patients to Day 30 T-cell functionality • Comparison of the relationship between change from Day 30 in AZD7442 serum level, T- cell function and World Health Organization Ordinal Scale

	
(WOS) for SARS-CoV-2 disease severity in all cancer patients with documented PCR positive SARS-CoV-2 infection
 
 • Comparison of the relationship between change from Day 30 in AZD7442 serum level, T- cell function and World Health Organization Ordinal Scale (WOS) for SARS-CoV-2 disease severity in all cancer patients with documented RT-PCR positive SARS-CoV-2 infection based on type of cancer treatment.

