17.5 Missing Data

There are several potential missing data considerations within this study. These are outlined as follows with associated methods of handling the missing information.

- Serum AZD7442 concentration: For both the ITT and PP populations, if a patient has serum AZD7442 at Day 30 and Day 90 but does not have an additional timepoint at Day 180 then the value for the missing serum AZD7442 concentration data point at Day 180 will be predicted from the linear regression of the log

AZD7442 serum concentration from the Day 90 analysis. Otherwise, the missing AZD7442 serum concentration data will be treated as missing data.

- SARS-CoV-2 infection: Will be determined through the documentation of SARS-CoV-2 diagnosis either through SARS-CoV-2 by Rt-PCR test, the medical record or claims information. Multiple locations of documentation will be considered a confirmed diagnosis.

- Clinical Outcome Assessment/Quality of Life Assessment: If data are missing through the survey collection process, then only the relevant measures will be calculated. Appropriate consideration of missing values will be addressed for time points comparison either through the non-inclusion of the patient outcome in that time point and/or within regression model assessment.

- RBG-IgG antibody level: Correlations will be determined where there is complete information only.

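### Change in AZD7442 level is referenced to Day 30 throughout, so the Day 270 and Day 360 changes cross the Day 180 redose, and the change at an infection draw is not a consistent exposure measure

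*Protocol*

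**What the plan says.** Section 17.9 uses change in log AZD7442 concentration twice: once to correlate with symptom severity, and once relative to change in clinical status within each disease cohort. Both times the change is "defined as the change over time from first measurement at Day 30 to Days 90, 180, 270 and 360". Day 30 after the first dose is thus the only reference for all four later visits.

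Section 9.3 states: "At Day 180 post-baseline, all patients will be administered a repeat dose of AZD7442 600 mg IM or IV". For that dose, "The window for this treatment will be +/- 5 days from the actual due date". Sampling follows its own schedule: "Site personnel will obtain blood for serum concentration of AZD7442 at days 30, 90, 180, 270 and 360 post-baseline", and "The window for these blood draws will be +/- 5 days from the actual due date". The order of the Day 180 sample and the Day 180 dose is not stated. The missing-data rule in 17.5 implies that the sample comes first, because "the value for the missing serum AZD7442 concentration data point at Day 180 will be predicted from the linear regression of the log" concentration, which presumes that the level is still falling.

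The T-cell objectives in 4.1 use the same reference in patients with RT-PCR positive infection: "Assess the relationship between change from Day 30 in AZD7442 serum level", together with T-cell function and WHO ordinal severity (WOS). The sub-study endpoints in 16.1 repeat it. The infection sample is taken about 10 days after the positive test, or whenever the patient can safely return (9.3).

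**The concern.** A change from one fixed reference is easy to read as decline. Here it is decline only up to the redose. After Day 180 the same quantity is decline from the first dose plus the whole contribution of the second. The protocol lists the four changes side by side as one variable, without resetting the reference, separating the two dosing intervals or adjusting for time since last dose.

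At stake is the meaning of the planned correlations with symptoms and clinical status. In the sub-study it is the relation between antibody level and disease severity among infected patients. There each patient contributes a sample at a personal calendar time, so mixing of times since dose cannot be avoided by analysing visit by visit.

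**Working it through.** The plan states no figure on this point, so there is none to reproduce. The check is an illustration under stated assumptions.

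**Inputs from the protocol.** Equal 600 mg doses at Days 0 and 180; samples at Days 30, 90, 180, 270 and 360; no AZD7442 sample at Day 210; windows of 5 days either side for both draw and redose.

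**Assumptions.** Half-life T of 45, 60, 90 or 120 days (section 23.4 gives no number), mono-exponential decline, full redose, immediate absorption.

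**Formula.** With k = ln 2 / T, C(t) = exp(−kt) up to the redose and C(t) = exp(−kt) + exp(−k(t − 180)) after it.

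**Scheduled visits.** Level relative to Day 30, and the matched ratio:

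| T (days) | Day 90 | Day 180, pre-redose | Day 270 | Day 360 | Day 270/90 and Day 360/180 |
|---|---|---|---|---|---|
| 45 | 0.40 | 0.10 | 0.42 | 0.11 | 1.06 |
| 60 | 0.50 | 0.18 | 0.56 | 0.20 | 1.12 |
| 90 | 0.63 | 0.31 | 0.79 | 0.39 | 1.25 |
| 120 | 0.71 | 0.42 | 0.96 | 0.57 | 1.35 |

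The pattern is a sawtooth: Day 270 shows less apparent decline than Day 90 in every row. Algebraically, C(270)/C(30) = exp(−60k) × (1 + exp(−180k)), which is the Day 90 ratio multiplied by the matched ratio. Day 360 stands in the same relation to Day 180. A single straight line through the log changes from Day 30 to Day 360 recovers only 31%, 24% and 15% of the true elimination slope at T = 60, 90 and 120.

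**Day 180 order.** At T = 90 the log change is −1.16 if the sample precedes the redose. If the redose is given on Day 175 and the sample is drawn 5 to 10 days later, all within the windows, the change is +0.42 to +0.39, so the sign reverses.

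**Infection draws.** Compare the same patient drawn on Day 180 before the redose (positive on Day 170) and on Day 200 (positive on Day 190):

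- T = 45: C(200)/C(180) = 0.781/0.0625 = 12.5
- T = 60: 0.893/0.125 = 7.1
- T = 90: 1.071/0.25 = 4.3
- T = 120: 1.206/0.354 = 3.4

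Two further cases have no clear meaning. A draw before Day 30 gives a change that runs backwards in time. A patient positive on Day 175 and redosed on Day 180 has a draw near Day 185 that includes drug given after the infection; 9.3 keeps symptomatic infected patients in all study procedures.

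**If scheduled visits were pooled.** A simulation of 40,000 patients per scenario (T = 60, 90, 120; between-patient half-life CV 15% or 30%; residual log SD 0.1, 0.2, 0.3) puts the share of variance in the changes that is due to visit at 28% to 81%. It exceeds half in 5 of 6 scenarios at 60 days, 3 of 6 at 90 and 2 of 6 at 120, so 10 of 18.

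**If analysed visit by visit.** At T = 90 the change still correlates with the patient's elimination rate: −0.25 to −0.84 at Day 270 and −0.46 to −0.95 at Day 360.

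**Check of the remedy.** Within an interval, the log change from Day 90 to a pre-redose Day 180 and from Day 270 to Day 360 is −90k in both: −1.04, −0.69 and −0.52 at T = 60, 90 and 120. Both measure elimination only.

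**The case against.** Several counter-arguments stand.

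- A reader might infer that the change from Day 30 mainly records when the sample was taken. For scheduled visits the protocol does not support this. Section 17.9 never says that visits are pooled, and 17.12 leaves methods for other endpoints to case-by-case choice. At one visit all patients have nearly the same time since dose, so the redose is largely a common shift. The per-visit correlations above confirm that patient information survives.
- Nor are all four changes contaminated. Day 90 is elimination only, and so is Day 180 if drawn before the redose.
- A reader might also infer that the trial cannot answer whether six-monthly dosing keeps levels stable. That does not follow. The primary analysis (13.2, 17.6) models log concentration at each timepoint, and Day 270 versus Day 90 can be contrasted there. Observed levels at infection are also described under 17.10.
- Time since dose is a cause of exposure, not merely noise. The patient drawn before the redose really has several-fold less antibody, and that may matter for severity. Replacing the level by a residual for time since dose would remove real exposure differences.
- The size depends on the assumed half-life and on immediate absorption, and the 12-fold figure comes only from the shortest half-life.

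What these do not answer is that 17.9 states its definition explicitly and that it crosses a dose at two of four visits. Nor do they make the ratio to Day 30 interpretable for infection draws at arbitrary times. The rank-based comparisons across WOS groups in 17.8, as described, carry no timing covariate.

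**Conclusion.** The point holds in a limited form. The Day 270 and Day 360 changes defined in 17.9 span a second dose, do not measure decline and are not comparable with the Day 90 change. Day 180 is undetermined until the order of draw and redose is known. Confounding by sampling time in the symptom and clinical-status correlations arises if visits are pooled, which the protocol neither states nor excludes. For the infection-triggered samples in 4.1 and 16.1 the inconsistency is present whatever the handling of scheduled visits: about 12-fold to 3-fold for one patient between Day 180 pre-redose and Day 200, under half-lives of 45 to 120 days, mono-exponential decline and immediate absorption. The primary endpoint analysis is unaffected. This should be corrected, but it bears on supporting and sub-study analyses only.

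**What to change.** **Section 17.9.** Define change within each dosing interval: Day 30 to Days 90 and 180, and Day 270 to Day 360. State that the correlations are analysed by visit. Add the matched log-ratios Day 270/Day 90 and Day 360/Day 180 in patients who received both doses. A change from 30 days after the second dose cannot be formed, because no AZD7442 sample is scheduled at Day 210.

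**Day 180.** Use as Day 180 values only samples recorded as drawn before the redose, and flag the others.

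**Sections 4.1 and 16.1.** Use the observed log concentration at the infection draw, with time since the last actual dose as a covariate. Flag draws where a redose fell between infection and sampling. Keep change from Day 30 only as a secondary description. Using the observed level with a covariate, rather than a residual, leaves the real exposure difference visible.

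**Cost.** Wording and slightly more analysis, using samples already scheduled and the recorded dose and draw times. Patients who miss the redose drop out of the matched ratios, so their number should be reported beside them.

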	
antibodies, in particular subjects with a history of cancer who were treated with chemotherapy, immunotherapy, targeted therapy, other therapy or combination therapies.
 
Evaluations of real-world evidence are becoming increasingly important to healthcare providers and payers. These data analyses and interpretations are evolving in a direction that has the potential to become the standard for post-approval medication/vaccine evaluation including both comparative effectiveness and safety. In this program, the population will be broadly diverse with respect to age, gender, race, geography, socio-economic status, health literacy, and insurance coverage. This will allow for recruitment of patients considered to be comparable to those studied pre-approval but inclusive of the diverse nature of cancer patients.
 
The program population will include a large number of patients with co-morbidities that may have a significant impact on their ability to maintain therapeutic levels of AZD7442 over 12 months post-baseline and, as a result, prevent a symptomatic SARS-CoV-2 infection.
 
1.3 Rationale for Immunological Profiling Using T-Cell (Thymocyte Derived Lymphocyte) Functional Testing in Immuno-Suppressed Cancer Patients
 
Post initial administration of AZD7442, breakthrough SARS-COV-2 RNA by RT-PCR positive SARS-CoV-2 infections could result from either failure of AZD742 to provide protection and/or intrinsic T-cell (Thymocyte Derived Lymphocyte) dysfunction. Relative to the latter possibility, it is known that in normal, healthy, immune-competent subjects, there is a significant T-cell response to COVID-19 virus that can result in (1) CD4 T-cell production and secretion of cytokines that activate other immune cells including B-cells, CD-8 T-cells and macrophages to combat the viral infection and/or (2) CD8 T-cell production and release of cytokines which destroy virus-infected cells by either lysis and/or apoptosis. Unfortunately, the relationship between neutralizing antibodies and T-cell activation/secretion is unknown in immuno-suppressed cancer patients at baseline as well as in response to active SARS-CoV-2 infection. As part of this program, a sub-study has been designed to provide systematic information to help address this critical issue.

2.0
	
2.1 Primary Hypothesis

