17.6 Evaluations of Primary and Secondary Endpoints

The primary and secondary endpoints will be evaluated for the intent-to-treat and per protocol patient populations. The primary comparisons will be the serum concentration of AZD7442 at Days 30, 90, 180, 270 and 360 post-baseline. Serum concentration comparisons of the log-adjusted serum AZD7442 concentration will be analyzed using linear mixed models for repeated measures. Models will include disease category, overall dose, and dose/kg accounting for concomitant treatment regimen category along with appropriate treatment and time interactions. An unstructured covariance matrix will be assumed, however, in the event of non-convergence, compound symmetry, and AR (1), covariance structures will be attempted, in that order. The Least Square Means Differences, and their 95% CIs, will be reported for each timepoint (e.g., Days 30, 90, 180, 270, and 360 post-treatment).

Additional comparisons for Quality of Life (QoL) will be made between the disease category cohorts and concomitant treatment regimen categories. The disease category cohorts are solid tumor cancers and hematologic cancers. Concomitant treatment regimen categories will be defined as chemotherapy only, immunotherapy

only, targeted therapy only, other therapy/ combination therapy only. Differences in the primary endpoints will be assessed using a two-sided statistical significance level of 0.01, adjusting for planned multiple comparisons. All other differences will be assessed using a two-sided statistical significance level of 0.05.

The secondary endpoint comparisons will be made:

- between concomitant treatment regimen categories and
- between disease category cohorts

The between concomitant treatment regimen categories will account for the between disease category analyses. These secondary endpoint comparisons will be made using a logistic regression or linear mixed model accounting for potential patient and disease factors where appropriate. Additional secondary endpoints are as noted previously. The secondary endpoints will be analyzed for the Intent-To-Treat (ITT) population with a Per-Protocol (PP) sensitivity analysis.

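### Section 17.9 names factor analysis to find which patient characteristics relate to AZD7442 concentration; the method has no outcome variable, and age, gender and cancer duration have no firm model elsewhere

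*Protocol*

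**What the plan says.** Section 17.9 (Clinical Outcome Measurements) ends its list with "Factor analysis to determine which factors (e.g., age, gender, type of cancer, cancer duration, type treatment, etc.) are related to higher levels" of serum AZD7442. The bullet gives no model, no covariate set beyond the examples, and no summary measure.

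Three other places bear on the same question.

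- Section 17.6: "Serum concentration comparisons of the log-adjusted serum AZD7442 concentration will be analyzed using linear mixed models for repeated measures". On covariates it says: "Models will include disease category, overall dose, and dose/kg accounting for concomitant treatment regimen category along with appropriate treatment and time interactions". It reports least-squares mean differences with 95% confidence intervals at each time point. For secondary comparisons it also allows adjustment for patient and disease factors where appropriate, without naming them.
- Section 17.11 compares baseline attributes between disease cohorts and treatment regimens, then states: "Any attributes with significant differences will be considered for inclusion as factors in logistic regression and linear model analyses".
- Section 17.12, on other endpoints: "Such approaches may include χ^2 cross-tabulations, t-tests, ANOVAs, negative-binomial regressions, logistic regressions, mixed model for repeated measures and linear regression". Factor analysis is not on that list.

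**The concern.** The bullet asks a regression question: which observed characteristics go with higher values of a named outcome. The method it names does something else. Factor analysis takes a correlation matrix and represents it through a small number of unobserved factors. Its output is a table of loadings, and its fit statistics concern how many latent factors are needed. No variable is the response, no characteristic is adjusted for the others, and no characteristic receives an effect size with a confidence interval. Gender, type of cancer and type of treatment are also binary or nominal, which standard factor analysis handles poorly.

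At stake is whether the trial can report, for age, gender and cancer duration, how much concentration differs and how precisely that is known. Concentration is the variable behind the primary endpoint, and Section 1.2 expects patients to have "co-morbidities that may have a significant impact on their ability to maintain therapeutic levels of AZD7442 over 12 months post-baseline". The link to that rationale is indirect, because 17.9 does not name comorbidities among its examples.

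**Working it through.** The plan gives no figure on this point, so there is none to reproduce. The check sets the sections side by side, then illustrates the difference between the methods on assumed data.

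**Step 1: which of the five named characteristics already have a model of concentration.**

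| Characteristic in 17.9 | In the 17.6 model of log concentration | Route through 17.11 |
|---|---|---|
| Type of cancer | Yes, as disease category | Defines the cohorts compared |
| Type of treatment | Yes, as regimen category | Defines the regimens compared |
| Age | Not named | Considered only if it differs between cohorts or regimens |
| Gender | Not named | Same condition |
| Cancer duration | Not named | Same condition (time from initial diagnosis) |

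Two of five are covered, so 5 − 2 = 3 remain. The 17.11 condition does not close the gap. It screens on imbalance between groups, not on relation to concentration, so a characteristic that predicts concentration strongly but is balanced across cohorts and regimens would not be considered. Section 17.12 is permissive and does not tie itself to the 17.9 bullet. The 17.6 allowance for patient factors where appropriate names none.

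**Step 2: illustration on one simulated data set per scenario.** All inputs are assumptions, not protocol values, apart from n = 1,500 and a 20% hematologic share, which match the planned enrollment. The covariates were age, cancer duration, sex (50%), hematologic disease, chemotherapy (30%) and weight. Log concentration either depended on none of them, or fell by 0.5 with hematologic disease and by 0.3 with sex, with residual SD 0.5. A two-factor principal-axis factor analysis was compared with linear regression.

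- *Factor analysis of the covariates alone:* the loadings were identical in both scenarios. They must be, because concentration is not an input.
- *Factor analysis with concentration added as a seventh variable, effects present:* on the first factor, concentration loaded 1.06, hematologic disease −0.31 and sex −0.23. The implied correlation of concentration with hematologic disease is the sum of loading products, 1.06 × (−0.31) + (−0.07) × 0.06 = −0.33. From the simulation inputs, Var(log concentration) = 0.5² × 0.16 + 0.3² × 0.25 + 0.5² = 0.3125, so the SD is 0.559 and the true correlation is −0.5 × 0.4 / 0.559 = −0.36. The loadings therefore carry a hint of the marginal association, but no adjusted effect and no test. The solution is also improper: the communality of concentration is 1.06² + 0.07² = 1.13, above 1.
- *Linear regression, effects present:* −0.48 for hematologic disease (true −0.5) and −0.28 for sex (true −0.3), each with a p-value that prints as 0.0000. Chemotherapy, which had no true effect, came out at p = 0.0145. That is a chance result in a single run, and a reminder that several covariates mean several tests.

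The illustration shows what kind of output each method gives. It says nothing about detection rates in this trial.

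**The case against.** The strongest reply is that the bullet is a misnomer. It names an outcome and a list of observed characteristics, and it mentions no latent constructs, loadings or rotation. Section 17.11 uses the word factors to mean regression covariates, and the methods listed in 17.12 contain no latent-variable technique. Read that way, the sponsor means an analysis of factors and will fit a regression; covariate choice for such an analysis commonly belongs in the SAP, which is not shown.

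Much of this stands. Regression is probably what is intended, and the detailed covariate list need not be in the protocol. What does not fall away is that the protocol states a specific method, and it is the wrong one for the stated purpose. An SAP that follows the text inherits the mismatch; one that uses regression departs from the text.

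A reader might also infer more than the documents support:

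- *That factor analysis could reveal nothing about concentration.* Too absolute: if concentration is entered as a variable, co-loading gives a crude indication, as Step 2 shows.
- *That the trial would miss major predictors such as hematologic disease or body weight.* Not so: 17.6 models disease category directly and brings weight in through dose/kg, with confidence intervals for the differences it reports.
- *That the primary analysis is compromised.* It is not. The bullet sits among other outcome measurements, is not on the 14.1 list of secondary endpoints, and no sample size or significance level depends on it.

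**Conclusion.** The point holds as a minor correction to an ancillary analysis. Section 17.9 pairs a question about predictors of concentration with a method that, in its standard meaning, has no outcome and gives no adjusted estimate, confidence interval or test. The practical gap is three of the five named characteristics: age, gender and cancer duration. For these no other section firmly commits to a model of concentration. This rests on reading factor analysis in its usual statistical sense and on the protocol alone; an SAP that specifies a regression would remove the practical consequence but not the wording error. No numerical loss of power or bias is claimed.

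**What to change.** In 17.9, replace the factor analysis bullet with a sentence such as: *Log AZD7442 concentration at Days 30, 90, 180, 270 and 360 will be analyzed in a multivariable linear mixed model that extends the model of Section 17.6 (disease category, regimen, dose/kg, time) with age, gender and cancer duration, entered whether or not they differ between cohorts or regimens; adjusted geometric mean ratios with 95% confidence intervals will be reported.* Any further characteristics now covered by the open-ended wording of the bullet should be named or left out. If the bullet is meant to serve the Section 1.2 rationale, comorbidities should be among those named.

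The cost is one sentence. Age, gender and time from initial diagnosis are already among the attributes listed in 17.11, and the model builds on one already planned. Visits, sample size and the primary analysis do not change.
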